accessible by researchers. From July 2005, the Prescribed Drug Register (PDR), covers date and amount of medication prescribed and dispensed to the patient. It also stores personal identification number, which enables linkage to other registers. The National Patient Register (NPR) covers inpatient care episodes and outpatient visits, including information of procedures (i.e. surgery) and diagnosis codes. The Swedish Cancer Register (SCR) (since 1958) contains tumor and pathology data from all patients diagnosed with cancer in Sweden. The national Cause of Death Register (CDR) (1961) contain information on the cause of death.

Combining data from these four registers creates an opportunity to derive patterns of duration of treatment and overall survival for the full Swedish mRCC cohort.

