### 8.2. Setting

The data used for the analyses includes all patients aged  $\geq 18$  years with at least one filled prescription of an oral targeted therapy relevant for treating mRCC registered in the Swedish Prescribed Drug Register between 01 July 2005 (there is no data available in the register before this date) and 31 December 2019. The Anatomical Therapeutic Chemical (ATC) codes for the oral drugs relevant for treating mRCC are the following: L01XE04 (sunitinib), L01XE05 (sorafenib), L01XE11 (pazopanib), L01XE17 (axitinib), L01XE10 (everolimus), L01XE26 (cabozantinib), L01XE34 (tivozanib), L01XE29 (lenvatinib).

Selecting patients based on dispensed prescriptions ensure that all patients that have prescriptions on the relevant drugs are included in the analyses. The first identified prescription date will correspond to the patient's index date that is relevant for capturing the age.

The PDR does not provide any information on mRCC, which is the area of interest in this study. The analysis therefore combines the PDR, the SCR and the NPR with the aim to identify the mRCC cohort. The patients identified in the PDR that also are identified in the SCR with the International Classification of Diseases and Related Health Problems

PFIZER CONFIDENTIAL

(ICD)-7 diagnosis codes I800 or I809 and ICD-10 codes C64.0 and C64.9 from 01 January 2000 until 31 December 2019; excluding ICD-7 code I801 (cancer of the renal pelvis) will be included in the analysis set.

The mRCC cohort derived above will then be further restricted into two different analysis sets that will be used to carry out the analyses.

[figure not shown]
- Analysis Set 1: patients treated with sunitinib in the first line mRCC setting
- Analysis Set 2: patients treated with axitinib in the second line mRCC setting

Analysis Set 1 will be derived in the following way, from the full mRCC cohort described above, individuals will be selected that have sunitinib as the first filled prescription (the earliest date) of the relevant drugs: (sunitinib), L01XE05 (sorafenib), L01XE11 (pazopanib), L01XE17 (axitinib), L01XE10 (everolimus), L01XE26 (cabozantinib), L01XE34 (tivozanib), L01XE29 (lenvatinib), and L03AB (cytokines medication). L03AB used to be a common treatment for this patient group in the beginning of the investigated period and is therefore needed to identify the correct treatment line.

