**Table 1. Overview of study variables**

Variable	Role	Data source(s)	Operational definition
Total number of sunitinib 1L patients	Outcome	Prescription Register	Number of sunitinib users with at least one filled prescription (in total and per year over time)
Number of sunitinib 1L 4:2 schedule users	Outcome	Prescription Register	Number of sunitinib users that started on a 4:2 schedule and never had a modification in the schedule (total and per year over time)
Number of sunitinib 1L 2:1 schedule users	Outcome	Prescription Register	Number of sunitinib users that started on a 2:1 schedule and never had a modification in the schedule (total and per year over time)
Number of sunitinib 1L patients that was switched from a 4:2 schedule to a 2:1 schedule	Outcome	Prescription Register	Number of sunitinib users that started on a 4:2 schedule and later was switched to a 2:1 schedule, in total and per year over time

PFIZER CONFIDENTIAL

Total number of axitinib second line patients	Outcome	Prescription Register	Number of axitinib 2L users with at least one filled prescription (in total and per year over time)
Gender	Baseline characteristics	Prescription Register	Male/Female (binary)
Age	Baseline characteristics	Prescription Register	Age will be defined as age at the date of first filled prescription of relevant mRCC medication (continuous; years).
Year of treatment initiation	Baseline characteristics	Prescription Register	Defines the year the treatment was initiated.
Region	Baseline characteristics	Prescription Register	County council of the prescribing physician at first prescription date (categorical), see Table 6 in Annex 3
Time to treatment discontinuation	Outcome	Prescription Register	Time from date of first filled prescription to the end of the prescribed supply, or prescription of other ATC code or death if either of these happen before (details in Section 8.2).
Overall survival	Outcome	Cause of Death Register, Prescription Register	Time from date of first filled prescription of the relevant drug to date of death (number of days) where death is defined as all-cause death; If no date of death is recorded, data is censored at latest available date in data.

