**Table 2. Overview of data sources**

Type of register	Name	Data holder	Start of data collection	Variables
Patient register	Swedish National Patient Register	NBHW	1987/2001	Diagnosis codes (ICD-9/10), dates, procedure codes and types of visit
Prescription register	Swedish Prescribed Drug Register	NBHW	2005	Dispatch dates, type of medication (ATC codes), strengths and dosages
Information on mortality	Swedish Causes of Death Register	NBHW	1961	Date and cause of death (ICD-10)
Cancer register	Swedish Cancer Register	NBHW	1958	Morphological diagnosis of the tumour (ICD-O/3)

The individual data will be extracted from the PDR and merged with the data from the SCR and the NPR using the personal identification numbers (PINs). The data extraction will cover all patients aged  $\geq 18$  years with at least one filled prescription of an oral targeted therapy relevant for treating mRCC registered in the Swedish Prescribed Drug Register between 01 July 2005 (there is no data available in the register before this date) and 31 December 2019. The Anatomical Therapeutic Chemical (ATC) codes for the oral drugs relevant for treating mRCC are the following: L01XE04 (sunitinib), L01XE05 (sorafenib), L01XE11 (pazopanib), L01XE17 (axitinib), L01XE10 (everolimus), L01XE26 (cabozantinib), L01XE34 (tivozanib), L01XE29 (lenvatinib).

PFIZER CONFIDENTIAL

The PDR does not provide any information on mRCC, which is the area of interest in this study. The analysis therefore combines the PDR, the SCR and the NPR with the aim to identify the mRCC cohort. The patients identified in the PDR that also are identified in the SCR with the International Classification of Diseases and Related Health Problems (ICD)-7 diagnosis codes I800 or I809 and ICD-10 codes C64.0 and C64.9 from 01 January 2000 until 31 December 2019; excluding ICD-7 code I801 (cancer of the renal pelvis) will be included in the analysis set.

The two analysis sets described in Section 8.2 will be derived and used in the analyses.

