### **8.7. Data analysis**

An overview of the planned analyses are presented in this section. In general, the study is descriptive and does not involve hypothesis testing. Any major modifications of primary endpoint definitions or their analyses would be reflected in a protocol amendment.

Time-to-event analyses will be carried out using standard Kaplan-Meier methods. Kaplan-Meier survival functions will be estimated with relevant events as failure. Time-to-event tables

PFIZER CONFIDENTIAL

and Kaplan-Meier curves will be presented. Log-Rank tests will be used to assess differences across cohorts. In addition, to explore potential determinants of persistence /drug survival and to adjust for differences across cohorts, semi-parametric cox-proportional hazard models will be deployed based on different covariates.

Relevant events for this study include:

- Time to treatment discontinuation
- Death

Time-to-event tables will present:

- Failed/Censored n (%).
- Median time to event.
- 95% confidence intervals of median.
- The 25th and 75th percentiles (q1 and q3).
- Min and max.
- n at risk by unit.
- Time point estimates and 95% Confidence Intervals (CI)by unit.

[figure not shown]
As described in Section 8.2 the analyses will be carried out based on two analysis sets.

Analysis Set 1 consists of all patients indentified with sunitinib as the first line treatment.

Analysis Set 2 consists of all patients indentified with axitinib as the second line treatment.

The Table 4 below displays the output from the time to treatment discontinuation and overall survival analyses that will be carried out based on Analysis Set 1. The output will be presented for three different dosing schemes of interest, patients that started on a 4:2 schedule and that did not switch, patients that started on a 4:2 schedule but later switched to a 2:1 schedule and patients that started on a 2:1 schedule and did not switch. Output will also be presented as Kaplan Meier (KM) curves.

PFIZER CONFIDENTIAL

[figure not shown]

To explore potential determinants drug survival and to adjust for differences across cohorts, semi-parametric cox-proportional hazard models will be deployed based on the following covariates: age, gender, year of treatment initiation, region.

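### The cancer-register morphology is extracted but never used, so non-RCC kidney tumours can enter the mRCC cohort and RCC subtype is neither described nor adjusted for across the sunitinib schedule groups.

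*Combined protocol and SAP*

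**What the plan says.** The title, the objectives in section 7 and both analysis sets in section 8.2 concern metastatic renal cell carcinoma.

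Cohort entry in section 8.2 has two parts:

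- **Drug.** Adults "with at least one filled prescription of an oral targeted therapy relevant for treating mRCC". Analysis Set 1 then requires sunitinib as the first relevant drug, and Analysis Set 2 requires axitinib as the second.
- **Diagnosis.** A Cancer Register record with "diagnosis codes I800 or I809 and ICD-10 codes C64.0 and C64.9 from 01 January 2000 until 31 December 2019". The only diagnostic exclusion is ICD-7 I801, the renal pelvis, which is also a site.

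Section 8.4 repeats the diagnostic rule and adds nothing on cell type. The National Patient Register is said to help identify the cohort, but no rule using it is given.

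Morphology is available. Section 6 says that the Cancer Register "contains tumor and pathology data from all patients diagnosed with cancer in Sweden". Table 2 gives that register's variable as "Morphological diagnosis of the tumour (ICD-O/3"). Table 3 extracts ICDO3 and, as a separate field, ICDO10 (ICD-O/2-10).

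Table 1 lists four baseline characteristics: gender, age, year of treatment initiation and region. The Cox models in section 8.7 are "based on the following covariates: age, gender, year of treatment initiation, region", and the same list is given for both analysis sets.

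**The concern.** A kidney site code establishes a malignancy of the kidney. It does not establish that the tumour is renal cell carcinoma, or of which subtype. The plan obtains the field that could answer both questions and gives it no role. Two consequences follow.

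1. **Case definition.** A patient with a non-RCC kidney tumour and a qualifying prescription counts toward treatment duration and overall survival reported for mRCC.
2. **Comparison of schedules.** The Cox models are meant to adjust for differences between the three sunitinib groups (4:2 throughout, 4:2 then 2:1, and 2:1 throughout). None of the four covariates describes the tumour. If subtype mix differs between the groups, part of any difference in time to discontinuation or survival could reflect histology, and the planned tables would not show it.

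The second consequence matters more. It bears on the primary objective, and the drug requirement does nothing to reduce it, because a fill does not separate one RCC subtype from another.

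**Working it through.** **Tracing the variable.** The plan states no figure on this point to reproduce, so the first check is where morphology appears.

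| Place | Role of morphology |
|---|---|
| 8.2 and 8.4, cohort rule | None |
| Table 2 | Named as the Cancer Register's variable |
| Table 3 | Extracted (ICDO3; ICDO10 separately) |
| Table 1, baseline characteristics | None |
| 8.7, Cox covariates, both sets | None |
| Tables 4 and 5, outputs | None |
| 8.9, limitations | None; mentions only other malignancies treated with the same drugs |

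**Inputs for size.** From section 8.5: about 1,000 patients in Analysis Set 1 and about 300 in Analysis Set 2. The documents give no non-RCC share, subtype mix or hazard by histology, so everything else below is assumed. The 24-month RCC median overall survival is a round value; section 6 says only that survival with the newer therapies exceeds 2 years.

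**(a) Non-RCC tumours in the cohort.** Let a share p have h times the RCC hazard, with exponential survival and λ = ln 2 / 24 per month. The pooled median t solves

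(1 − p)·exp(−λt) + p·exp(−hλt) = 0.5.

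| p | Set 1 / Set 2 patients | Median, h = 1.5 | Median, h = 2 |
|---|---|---|---|
| 2% | 20 / 6 | 23.8 months (−0.8%) | 23.7 months (−1.4%) |
| 5% | 50 / 15 | 23.5 months (−2.1%) | 23.1 months (−3.6%) |
| 10% | 100 / 30 | 23.0 months (−4.1%) | 22.3 months (−7.0%) |

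The percentages do not depend on the 24 months. Under the same exponential model they would apply to time to discontinuation too, if non-RCC tumours carried the same relative hazard of stopping, which is a further assumption.

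**(b) Subtype imbalance between two schedule groups, with no true schedule effect.** Let a poorer-prognosis subtype with hazard ratio h make up share a of one group and b of the other. At time zero the ratio of the group hazards is

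(b·h + 1 − b) / (a·h + 1 − a).

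This ratio shrinks over time as the higher-risk patients fail first. The hazard ratio that an unadjusted Cox model would report is the value that sets its expected score to zero, taken here over 60 months with equal group sizes.

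| a, b | h | Ratio at time zero | Apparent Cox HR |
|---|---|---|---|
| 15%, 25% | 1.5 | 1.125/1.075 = 1.047 | 1.039 |
| 15%, 25% | 2 | 1.25/1.15 = 1.087 | 1.063 |
| 10%, 30% | 1.5 | 1.15/1.05 = 1.095 | 1.080 |
| 10%, 30% | 2 | 1.30/1.10 = 1.182 | 1.129 |
| 20%, 20% | 1.5 or 2 | 1.000 | 1.000 |

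**(c) Comparison with sampling error.** For an uncensored exponential sample, the 95% half-width of an estimated median is about 1.96·√(0.25/n) / (0.5λ). This is 2.1 months at n = 1,000 and 3.9 months at n = 300. The shifts in (a), 0.2 to 1.7 months, are smaller than either.

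**The case against.** The strongest reply is that the drug requirement already screens the cohort. A non-RCC kidney tumour must carry a qualifying site code, avoid the renal-pelvis exclusion, and belong to a patient dispensed one of a short list of targeted drugs in the right order. This stands for the case definition: such patients are probably few. It does not answer the point on subtype.

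Second, confounding needs subtype to differ between schedule groups. The literature summarised in section 6 links schedule changes to tolerability and adverse events, not to histology. That is fair, and with equal mix the bias is nil. But the plan as written cannot show whether the mix is equal.

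Third, section 8.9 admits selection and misclassification bias in general, and the study is described as explorative and descriptive. That is partial cover at most. Section 8.9 names neither kidney-tumour histology nor subtype, and section 8.7 still plans log-rank tests and adjusted models.

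Fourth, the morphology field may be incomplete. Section 8.8 gives near-complete coverage for the Cancer Register as a whole, not for this field. Table 3 holds two separate ICD-O fields, so ICDO3 may not be filled for all diagnoses from 2000 to 2019. A reader might infer that an RCC morphology code should become the main inclusion rule. The documents do not support that: if the field is less complete in some years, the rule would drop patients by diagnosis year and could create a new selection problem.

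**Conclusion.** The point holds and merits a change at moderate priority. The diagnostic rule uses site codes only, the extracted morphology has no role anywhere in the plan, and subtype is absent from both the baseline description and the adjustment.

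Two stronger readings go too far. One is that the cohort is selected on site codes alone; section 8.2 also requires a dispensed drug. The other is that non-RCC tumours do enter the cohort; no figure in the documents shows even one such patient, so the supportable statement is that they can.

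The size of any bias is unknown from the documents. With 2-10% non-RCC at 1.5-2 times the hazard, median overall survival falls by about 1-7%. With the assumed subtype imbalances, a null schedule effect appears as a hazard ratio of about 1.04-1.13, and as 1.00 if the mix is equal. Shares, imbalances, hazards and exponential survival are all assumed. The month figures are for overall survival, a secondary outcome; no separate estimate was made for time to discontinuation, the primary endpoint. The shift in the median is smaller than its sampling error. The case therefore rests on a correct case description and a visible, adjusted case mix at little cost, not on a demonstrated large bias.

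**What to change.** 1. In section 8.6, derive one morphology variable from the ICD-O fields already in Table 3 (ICDO3, with ICDO10 where it helps). Use four categories: clear cell RCC, other RCC, non-RCC and unspecified. Annex the code list.
2. Add the variable to Table 1 as a baseline characteristic. Report it, with its missingness, by schedule group for Analysis Set 1 and overall for Analysis Set 2.
3. Add it to the Cox covariates in section 8.7 for both sets, keeping unspecified as its own category.
4. Keep the site-code cohort as the main cohort. Add a sensitivity analysis that excludes tumours with a non-RCC morphology code.
5. If morphology proves too incomplete to use, report that and state it as a limitation in section 8.9.

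The cost is a code list, one derived variable and a few more model parameters (four categories add three). No new data request is needed. The extra parameters weigh more in Analysis Set 2, with about 300 patients, so the plan should say in advance how sparse categories will be combined.

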Analysis Set 2 will be derived in the following way, from the full mRCC cohort described above, individuals will be selected that have axitinib as the second filled prescription (the earliest date) of the relevant drugs: (sunitinib), L01XE05 (sorafenib), L01XE11 (pazopanib), L01XE17 (axitinib), L01XE10 (everolimus), L01XE26 (cabozantinib), L01XE34 (tivozanib), L01XE29 (lenvatinib). In addition, to secure that axitinib is used as a second line treatment (i.e. not third line), L03AB (cytokines medication) is not allowed to have been dispensed before axitinib.

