### **8.5. Study size**

An estimated 17,000 to 18,000 patients are diagnosed with RCC between 01 January 2000 and 31 December 2019, approximately 1,000 patients per year. Of these patients, an estimated 4,000 to 5,000 are registered with at least one relevant dispensed prescription for mRCC. Approximately 1,000 of these patients are estimated to have received sunitinib as first line treatment during the investigated period. For axitinib, approximately 300 patients are estimated to have received it in second line during the investigated period.

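### First-line sunitinib is set by the earliest visible fill with no minimum look-back, so treatment line may be wrong for an unknown share of the earliest starters

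*Combined protocol and SAP*

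**What the plan says.** Section 8.2 draws the cohort from patients with a fill of a listed oral drug "between 01 July 2005 (there is no data available in the register before this date) and 31 December 2019". They must also have a kidney cancer record in the Cancer Register dated "from 01 January 2000 until 31 December 2019".

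For Analysis Set 1, "individuals will be selected that have sunitinib as the first filled prescription (the earliest date) of the relevant drugs", and the list is widened to include cytokines (L03AB). The reason given is that "L03AB used to be a common treatment for this patient group in the beginning of the investigated period". From this the plan concludes that counting cytokine fills "is therefore needed to identify the correct treatment line".

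Sections 8.2, 8.2.1, 8.4, 8.6 and 8.7 contain no look-back, washout or minimum observation time before the first sunitinib fill. The one sensitivity analysis planned (Section 8.2.1) changes the grace period to 60 and 120 days. Section 8.9 acknowledges that drugs given in hospital are not visible and that line is judged from treatment order without progression data. It does not mention dispensing history lost before July 2005.

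**The concern.** The L03AB rule can only exclude a patient whose cytokine fill appears in the register. For someone starting sunitinib soon after the register opened, there is little history to search. That is also the part of the period in which the plan says cytokines were common. A patient diagnosed in, say, 2003, whose cytokine fills all ended before 1 July 2005, meets the Set 1 definition as soon as sunitinib is the first visible fill.

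First-line status defines the population for the primary endpoint (Section 8.1), which is analysed by Kaplan-Meier within schedule groups (Section 8.7, Table 4). If pretreated patients sit in those groups, the curves and medians describe a mixture of lines, and the plan contains nothing that would reveal it. Year of treatment initiation is a covariate in the Cox models, but it does not restore the correct line and does not enter the Kaplan-Meier estimates.

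**Working it through.** **Inputs from the documents**
- Visible dispensing: 1 July 2005 to 31 December 2019 (Section 8.2). This is 14.5 years × 12 = 174 months, taken from the calendar dates rather than from the 180-month ceiling in Section 8.1.
- Diagnosis window before the register opens: 1 January 2000 to 30 June 2005, or 5.5 × 12 = 66 months. A patient may have up to 66 months of diagnosed disease with no visible dispensing.
- Expected Set 1 size: "Approximately 1,000 of these patients are estimated to have received sunitinib as first line treatment during the investigated period" (Section 8.5). The plan gives no formula or yearly counts, so this figure is taken as stated and cannot be reproduced.

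**Step 1: starters with short history**

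Starters with under L months of history = 1,000 × (L / 174) × f. Here f is an assumed early-uptake factor, with f = 1 meaning even uptake.

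| L (months) | f = 0.5 | f = 1 | f = 2 |
|---|---|---|---|
| 6 | 17 | 34 | 69 |
| 12 | 34 | 69 | 138 |
| 24 | 69 | 138 | 276 |

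At L = 12 and f = 1: 1,000 × 12 / 174 = 69, or 6.9%. A 12-month restriction would leave about 931 patients and a 24-month restriction about 862.

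**Step 2: dependence on the first sunitinib fill**

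If sunitinib was first dispensed g months after the register opened, and uptake was even from then on, starters with under 12 months of history = 1,000 × (12 − g) / (174 − g), and zero once g is 12 or more.
- g = 0: 69
- g = 6: 1,000 × 6 / 168 = 36
- g = 12 or more: 0

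The documents do not give g.

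**Step 3: from short history to misclassified**

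Short history is not misclassification. Only those whose earlier treatment is wholly unseen are affected. Assume, with no figure in the documents to support it, that 10% to 50% of the short-history starters are in that position.
- L = 12, f = 1: 0.10 × 69 = 7 to 0.50 × 69 = 34 patients, or 0.7% to 3.4% of Set 1.
- L = 12, f from 0.5 to 2: about 3 to 69 patients, or 0.3% to 6.9%.
- With g of 12 or more, the number from this 12-month group is zero.

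**Step 4: what a restriction achieves**

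A 12-month rule admits first fills from 1 July 2006. A patient whose cytokines ended in early 2005 and who began sunitinib in autumn 2006 passes it. A 24-month rule (first fills from 1 July 2007) removes that patient. Restricting to diagnoses on or after 1 July 2005 means that the whole period since diagnosis falls within the register's coverage, so no dispensed treatment given after diagnosis is lost to the register's start date. The size of that subset cannot be worked out from the documents.

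**The case against.** The strongest reply is that the L03AB rule works for most of the period. Cytokines filled on or after 1 July 2005 are captured and do exclude the patient. The plan's remark about common use concerns the investigated period, which is the visible one. Any interval between the register opening and the first sunitinib fill is a built-in look-back. The study is exploratory and descriptive, Section 8.2 states when the register begins, Section 8.9 names misclassification bias in general terms, and Table 1 already plans yearly counts.

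Much of this stands. It limits the problem to patients whose cytokine fills all fell before July 2005, and it allows the number to be zero. It does not close the gap. The rule as written can label such patients first line, the general wording in Section 8.9 does not identify them, and yearly counts show how many early starters there are but not whether the results depend on them.

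A reader might infer more than the documents support:
- **That some Set 1 patients were already on sunitinib when the register opened.** Nothing says sunitinib was dispensed in Sweden before July 2005.
- **That the error works against the 4:2 cohort.** This would need the early years to be mostly 4:2 and pretreated patients to do worse. The plan establishes neither.
- **That axitinib is affected in the same way.** The Set 2 condition that "L03AB (cytokines medication) is not allowed to have been dispensed before axitinib" also has no stated look-back, but the documents give no basis for thinking any Set 2 patient is misclassified because of it.

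**Conclusion.** The point holds as a gap in the definition and in the planned checks. Treatment line may be wrong for an unknown share of the earliest sunitinib starters. It would go too far to say that first-line status is wrong for early starters as a group, or that the cytokine rule fails in those years.

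The figure of about 69 in 1,000 with under 12 months of history rests on even uptake from the first day of the register. The 7 to 34 misclassified patients rest further on an assumed 10% to 50% with unseen pretreatment. With a late enough first sunitinib fill, no starter would have under 12 months of history.

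This does not justify mandatory exclusion in the base case. Any single cut-off is arbitrary, and a 12-month one still misses earlier cytokine courses. It does justify a pre-specified sensitivity analysis, because first-line status defines the primary population and nothing now planned tests it.

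**What to change.** Keep all starters in the base case and make three additions.

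1. In Section 8.7, pre-specify a sensitivity analysis of time to treatment discontinuation and overall survival by schedule. Restrict it to Set 1 patients with a fixed minimum of visible register history before the first sunitinib fill (for example 12 and 24 months), or to those with a kidney cancer diagnosis date on or after 1 July 2005.
2. Report available look-back by start year, next to the yearly counts already planned in Table 1.
3. State in Section 8.9 that dispensing before July 2005 is not visible and that line may be misassigned for some of the earliest starters.

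The fields needed (diagnosis date, dispense date and ATC code) are already in Table 3, so the work amounts to date filters. The cost is a smaller sample in the sensitivity run only: about 931 and 862 of 1,000 under even uptake for the 12- and 24-month rules, and a number the documents do not allow to be estimated for the diagnosis-date rule.

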## **7. RESEARCH QUESTION AND OBJECTIVES**

The present study is an explorative retrospective study investigating treatment patterns and outcomes for sunitinib and axitinib mRCC patients in a nationwide population-based setting in sweden.

In more detail the primary objective is to:

- Investigate time to treatment discontinuation (treatment duration) for first line treatment with sunitinib for different treatment schedules: 4:2 (4 weeks on/2 weeks off) and 2:1 (2 weeks on/1 week off).

The secondary objectives are to:

- Investigate overall survival (OS) for first line treatment with sunitinib, for different treatment schedules, 4:2 (4 weeks on/2 weeks off) and 2:1 (2 weeks on/1 week off).
- For second line treatment with axitinib, investigate time to treatment discontinuation (treatment duration) and OS.

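### Analysis Set 2 leaves out cytokine-then-axitinib patients, who are second line by the Set 1 convention, and its wording on the second fill is ambiguous

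*Combined protocol and SAP*

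**What the plan says.** The secondary objective in Section 7 is unrestricted: "For second line treatment with axitinib, investigate time to treatment discontinuation (treatment duration) and OS". Section 8.2 labels the set in the same way: "Analysis Set 2: patients treated with axitinib in the second line mRCC setting".

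Section 8.2 then gives two selection rules.

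- **Set 1.** Patients qualify if they "have sunitinib as the first filled prescription (the earliest date) of the relevant drugs". The ordered list holds the eight oral targeted drugs plus L03AB. The reason given for listing L03AB is that it was common early in the period and "is therefore needed to identify the correct treatment line".
- **Set 2.** Patients qualify if they "have axitinib as the second filled prescription (the earliest date) of the relevant drugs". The list holds the same eight oral drugs but not L03AB. A separate condition follows: "L03AB (cytokines medication) is not allowed to have been dispensed before axitinib". Its purpose is "to secure that axitinib is used as a second line treatment (i.e. not third line").

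Section 8.7 describes Set 2 as all patients identified with axitinib as second-line treatment, and the column of Table 5 is headed as all second-line patients. Table 1 lists the total number of second-line axitinib patients, overall and per year, as an outcome. Section 8.5 expects about 300 of them.

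**The concern.** The two sets handle cytokines differently. In Set 1 a cytokine takes a place in the sequence and so counts as a line. In Set 2 it takes no place and instead disqualifies the patient. The ban does what it is meant to do for a patient who had a cytokine, then an oral drug, then axitinib. It also removes a patient who went from a cytokine straight to axitinib, which is second line by the Set 1 convention. The protocol neither mentions nor justifies this second effect. The treatment-line limitation in Section 8.9 concerns only the lack of progression data.

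At stake is whether the axitinib results match their label. Any patient left out this way lowers a reported count and changes the sample behind the Kaplan-Meier estimates for discontinuation and overall survival. The primary objective, on sunitinib, is not touched.

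The second issue is wording. For a first treatment, the first fill and the first drug coincide, so the Set 1 sentence is harmless. For a second treatment they do not, because most drugs are refilled. The Set 2 sentence should not leave the programmer to choose.

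**Working it through.** The figure of about 300 in Section 8.5 is given without inputs, so it can be neither reproduced nor refuted. The main check is one of logic.

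**Step 1: apply the rule to example sequences.** The benchmark is the Set 1 convention: order distinct treatments by first dispensing date, with cytokines counted, and call axitinib second line if it comes second. The Set 2 rule is applied in two readings: the second distinct listed drug, and literally the second fill of any listed drug. The cytokine ban applies in both.

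| Dispensing sequence | Second line by Set 1 convention? | In Set 2, distinct-drug reading | In Set 2, literal-fill reading |
|---|---|---|---|
| sunitinib, axitinib | yes | yes | yes |
| sunitinib three times, axitinib | yes | yes | no |
| cytokine, axitinib | yes | no | no |
| cytokine, sunitinib, axitinib | no (third) | no | no |
| sunitinib, cytokine, axitinib | no (third) | no | no |
| sunitinib, pazopanib, axitinib | no (third) | no | no |
| axitinib, axitinib | no (first) | no | yes |

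Under the distinct-drug reading, one row disagrees with the benchmark: cytokine then axitinib. That patient fails twice, because axitinib is only the first drug on the Set 2 list and because L03AB came before it. Lifting the ban alone would therefore not admit the patient; L03AB also has to join the list.

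Under the literal-fill reading two more rows go wrong, in opposite directions. A patient who refilled the first-line drug is lost, and a first-line axitinib patient enters at the second axitinib fill.

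**Step 2: size of the cytokine-then-axitinib group.** The documents give no number, so a share f of all second-line axitinib patients has to be assumed.

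- If 300 is the total before the exclusion, the number lost is 300 × f.
- If 300 is the number left after it, the number lost is 300 × f / (1 − f).

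| Assumed f | 300 is the total | 300 is what remains |
|---|---|---|
| 0% | 0 | 0 |
| 1% | 3 | 3.0 |
| 2% | 6 | 6.1 |
| 5% | 15 | 15.8 |

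Nothing in the documents favours any value of f over zero. Section 8.2 says cytokines were common at the beginning of the investigated period, which points towards a small share.

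**The case against.** The strongest reply is that the two sets differ less than they seem to. Listing L03AB in Set 1 has one practical effect: a patient with a cytokine before sunitinib is removed. The Set 2 ban does the same for axitinib. Both sets thus require no cytokine before the index drug, and they part only on the direct cytokine-to-axitinib sequence. The restriction is stated openly, and a set limited to axitinib after an oral targeted drug is more homogeneous and defensible. The analysis is also descriptive, secondary and single-group.

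Much of this stands. It limits the point to one sequence and makes the restriction a legitimate option. It does not remove the mismatch: the reason given covers third-line use only, while the objective, Section 8.7, Table 1 and Table 5 all describe second-line axitinib without that limit.

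Two stronger readings are tempting, and the documents support neither.

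- A reader might infer that Set 2 is not the second-line population at all. Under the natural reading, every patient in it is second line by dispensing order, and the third-line sequences are correctly kept out. What is missing is one subgroup.
- A reader might infer that the plan selects on individual fills, so that nearly everyone with two or more first-line fills drops out. The reference to the earliest date among the relevant drugs, the Set 2 label, the stated purpose of the ban, the account of line in Section 8.9 as the order of treatments received, and the expected 300 patients all indicate the second distinct drug. The text is ambiguous; it does not show a plan to select on fills.

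**Conclusion.** The point holds as a minor inconsistency in the definition of Set 2. The rule goes beyond its stated purpose and excludes patients whose only earlier treatment was a cytokine. They are second line by the Set 1 convention and belong to the population that Set 2, Table 1 and Table 5 claim to describe. This conclusion rests on the text alone and assumes only that cytokines count as a line in both sets, as Section 8.2 says for Set 1.

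The number affected is unknown and may be near zero. The range of 0-15 of about 300 assumes a share of 0-5% and is an illustration, not an estimate. No material effect on the reported survival or discontinuation times can be shown from the documents.

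The reference to the second fill is a separate wording defect. It needs clarifying because its literal reading would give a wrong dataset, not because the plan is shown to intend it.

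**What to change.** Use one rule for both sets. Order each patient's distinct ATC codes by first dispensing date, on a single list of the eight oral drugs plus L03AB. Set 1 takes patients with sunitinib first; Set 2 takes patients with axitinib second. Drop the separate L03AB ban, which is then redundant: cytokine-sunitinib-axitinib and sunitinib-cytokine-axitinib both remain excluded as third line. The same sentence settles the ambiguity about fills. Tabulate Set 2 by preceding drug so that readers can see how many patients came from a cytokine.

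The cost is one rewritten sentence in Section 8.2 and one line of code. The downside is slightly more mixed prior therapy in Set 2, which the tabulation makes visible.

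If the restriction is intended, keep it but say so. Describe Set 2 in Sections 7, 8.2 and 8.7 and in Tables 1 and 5 as axitinib after one oral targeted drug without earlier cytokines, and report the number excluded for earlier L03AB. The wording on the second fill should still be changed to the second distinct drug.
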